2.1 Study Design

This is a two-armed cluster randomized controlled trial (RCT). Randomization occurred at the level of clinical centers, and was stratified by VA (Veterans Affairs) vs non-VA. Each arm had initially 7 clinical centers.

Clinical centers are randomized to one of two models of palliative care (PC) delivery: Model 1- Consultative PC (i.e., PC offered by a board-certified or board-eligible PC provider) or Model 2- Trained hepatologist led PC (i.e., PC offered by a trained hepatologist). An additional 5 centers were randomized (resulting in one in Model 1 and four in Model 2) and the study utilized 19 centers. Standardized protocols (including visit agenda) were be followed at each of the clinical centers to maintain intervention fidelity across sites in both models. For additional details, please refer to the study protocol.

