5.4 Secondary Efficacy Analyses

The secondary endpoints will be presented as descriptive statistics by visit.

Where appropriate (i.e., change from baseline can be calculated), models similar to the primary endpoint superiority analysis may be utilized for secondary endpoint analyses.

The healthcare utilization endpoints will be analyzed as follows. For scheduled and unscheduled hospital admissions within 30 and 90 days of enrollment, proportions will be analyzed using random effects logistic regression. Counts of hospital admissions, ER visits, and unscheduled office visits over 1 year will be analyzed using Poisson regression with robust standard errors and non-identity dispersion via generalized estimating equations.

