5.5 Exploratory Analyses

Survival will be summarized with Kaplan-Meier curves. Cox regression will be used for multivariable models, and robust standard errors will be used to account for within center clustering. ITT population will be used for the survival analyses.

Longitudinal analysis of FACT-Hep total score at 1, 2, 3, 6, 9 and 12 months will be performed utilizing the ITT population. Measurements of Fact-Hep will be set to missing after patients receive liver transplant or are transferred to hospice. A mixed model will be considered with center as a random effect and unstructured covariance structure (alternatively autoregressive covariance structure in case of a convergence difficulty) for repeated measurements of FACT-Hep over time within a patient. As in the primary analysis, the model will have treatment effect and adjustment for baseline FACT-Hep total score and VA status.

Additional covariates will be considered for multivariable modelling. MI will be utilized if more than 10% of missing records are present.

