12 STATISTICAL CONSIDERATIONS

12.1 General Analysis Conventions/Rules

Continuous variables will be summarized as number of observations, mean, standard deviation (SD), minimum, 25th percentile, median, 75th percentile, and maximum. Categorical variables will be summarized as frequency counts and percentages. Statistical comparisons will be performed using two-sided significance tests.

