Study Intervention Visits (for Both Model 1 and 2)	
All patient-caregiver dyads will receive the intervention at the initial visit, and at 1, 2, and 3 months from the initial visit. Initial/ 1st visit will occur within 6 weeks after informed consent. Ascertainment of baseline assessments will occur within 1 week before the scheduled initial visit. Informed consent, baseline assessments and initial visit may occur on the same day, but must follow this sequence.
 
1, 2 and 3 month visits can occur within a window period of 1 week (before/after) of their respective times from the initial visit. All study visits can occur in person, or remotely (by phone or telehealth with the institutional secure platform).
 
All caregiver visits can occur in person or by phone, as preferred by the caregivers. The initial caregiver visit can occur on the same day or within 1 week of patient's initial visit.

Data Collection for Study Visits (Month 1, 2 and 3)	All data collection (patients and caregivers) can occur by phone, paper forms or using online surveys. ESAS, DT and PHQ-9 are conducted before the study visit (within 1 week of visit), and all other assessments are conducted after the study visit (within 1 week after the study intervention visit)
Data Collection during Follow Up	Study follow up data collection will be conducted at 6, 9 and 12 months, by phone, paper or online, within 1 week/ 7 days (before/after) of the due date.
Number of Patient Caregiver dyads	936 patients with a caregiver when available (n=563) will be enrolled. We aim to recruit approximately an equal number of patients from each of the centers. The study will have power (83.2%) for the primary analysis to detect a minimally clinically important difference of 9 points in QOL change (baseline to 3 months) between the two randomized arms.
Number of Sites	19 Clinical Centers (8 VA and 11 non-VA Academic Centers).

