## Protocol Version 4.0

hypothesis will be assessed first and only if such superiority is not demonstrated then the non-inferiority (NI) analysis will be performed. Non-inferiority (with the pre-specified NI margin  $\text{DELTA}=4$ ) will be claimed when  $L > -\text{DELTA}$ , where  $L$  is the lower limit of two-sided 95% confidence interval for the above- mentioned coefficient for the treatment indicator.

A *supplementary analysis* will involve multivariable analysis with covariate adjustment of the treatment effect performed with the mixed linear regression model as above but with inclusion of additional baseline covariates as fixed effects. The regression model will be evaluated with respect to functional form of continuous covariates and use splines if needed to accommodate non-linear effect of a covariate.

The secondary outcomes which are summarized by a score will be analyzed in fashion similar to the primary analysis described above. Survival will be summarized with Kaplan-Meier curves and Cox regression will be used for multivariable models, and will consider a shared-frailty model to account for center clustering.

For subgroup analyses, using multivariable models, a potentially differential impact of the intervention will be assessed across complementary subgroups by testing for interaction of the treatment variable with a subgrouping variable. In addition to tests we will present estimated treatment effects and the corresponding 95%CI for subgroup/subset treatment effects.

Palliative care knowledge gained by the hepatologists will be assessed by summarizing the responses to pre post assessment questionnaires in the training program.

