Standards on Research Designs Using Clusters	HT-3	Report all prespecified HTE analyses and, at minimum, the number of post-hoc HTE analyses, including all subgroups and outcomes analyzed
	RC-1	Specify whether the study objectives, the interventions, and the primary outcomes pertain to the cluster level or the individual level
	RC-2	Justify the choice of cluster randomization
	RC-3	Power and sample size estimates must use appropriate methods to account for the dependence of observations within clusters and the degrees of freedom available at the cluster level
	RC-4	Data analyses must account for the dependence of observations within clusters regardless of its magnitude
	RC-5	Stratified randomization should be used when feasible

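### The one-year count analyses and the survival analysis rest on robust standard errors from 19 centers with no small-sample method specified, and the count analysis does not name center as the cluster

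*SAP*

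**What the plan says.** **Counts.** SAP 5.4 states that one-year counts of hospital admissions, ER visits and unscheduled office visits "will be analyzed using Poisson regression with robust standard errors and non-identity dispersion via generalized estimating equations". It gives no cluster unit, working correlation, small-sample correction, reference distribution or covariates for these models. Protocol 11.3 does not fill the gap: its text on secondary outcomes covers those summarized by a score, and then survival.

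**Survival.** For the Cox model, SAP 5.5 says that "robust standard errors will be used to account for within center clustering". Protocol 11.3 says that the survival analysis "will consider a shared-frailty model to account for center clustering".

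**Clusters.** SAP 2.1 says "Each arm had initially 7 clinical centers" and then "An additional 5 centers were randomized (resulting in one in Model 1 and four in Model 2) and the study utilized 19 centers". That makes 7 + 1 = 8 centers in Model 1 and 7 + 4 = 11 in Model 2. The protocol synopsis gives 8 VA and 11 non-VA centers.

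**Testing.** Under SAP 12.1, "Statistical comparisons will be performed using two-sided significance tests". Protocol 5.3 states superiority hypotheses for the ER-visit and unscheduled-visit rates, and SAP 12.6 declines any multiplicity adjustment. Among the methodology standards listed as met, Protocol section 12 includes "Data analyses must account for the dependence of observations within clusters regardless of its magnitude".

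**The concern.** The sandwich variance is justified as the number of clusters grows. With a treatment assigned by center, the information about its variance comes from 19 center-level residuals, 8 in one arm and 11 in the other. Fitting the model shrinks those residuals, so the uncorrected variance is too small on average. Comparing the result with a normal distribution then ignores how imprecisely that variance is estimated. Both errors make the test liberal and the interval too narrow.

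A difference in ER or office visits, or in survival, could therefore be reported as significant more often than its nominal level implies. The unnamed cluster in SAP 5.4 adds a second risk: a programmer who clusters on patient would leave out center correlation altogether.

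**Working it through.** **1. Is there a figure in the plan to reproduce?** The documents state no error rate for these analyses. The nearest figures are the primary-endpoint powers, 83.2% and 79.2%, which serve only to confirm the cluster layout. With SD 19.1, ICC 0.09, equal sites and an assumed 570 evaluable patients (30 per site):

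SE = √[(19.1² × 0.09 + 19.1² × 0.91/30) × (1/8 + 1/11)] = √[(32.83 + 11.07) × 0.2159] = 3.08.

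Superiority power = Φ(9/3.08 − 1.96) ≈ 83.2%; non-inferiority power = Φ(8.5/3.08 − 1.96) ≈ 78.8%. About 600 evaluable patients give 83.7% and 79.4%. The stated figures are attainable with 8 against 11 centers. The site counts needed to reproduce them exactly are not given.

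**2. Hand check of the sandwich.** Take equal sites, no covariates and site-level variance σ². The true variance of the arm difference is σ²(1/8 + 1/11) = 0.2159σ². The uncorrected sandwich has expectation σ²(7/8² + 10/11²) = σ²(0.1094 + 0.0826) = 0.1920σ². The ratio is 0.889, so the standard error is on average about √0.889 = 0.943 of its true value. A z cutoff of 1.96 then acts like 1.96 × 0.943 = 1.85. Referred to t on 17 df (19 centers less 2 parameters), this gives a two-sided rejection rate of about 8.2%. This is the favorable case: unequal sites and VA adjustment make it worse.

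**3. Null simulations, 8 against 11 centers.**

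- From the documents: 19 centers, up to 936 patients, and about 80% one-year survival (Protocol 5.5).
- Assumed: 700 to 936 patients analyzed; coefficient of variation (CV) of site size 0, 0.5 or 0.7; mean one event per patient-year with gamma overdispersion (shape 1); between-site rate CV 0.2 or 0.4; site log-hazard SD 0 or 0.3; 4 VA centers per arm; with and without VA adjustment.
- Runs per setting: 8,000 for counts with independence working correlation, 5,000 for counts with exchangeable correlation, and 3,000 for Cox. At a 10% rate the Monte Carlo standard error for Cox is √(0.1 × 0.9/3000) ≈ 0.5 percentage points.

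Rejection at nominal 5%, center-clustered, uncorrected, z-test:

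| Site-size CV | Counts (independence) | Cox |
|---|---|---|
| 0 | 8.5–10.3% | 7.8–9.6% |
| 0.5 | 9.9–12.3% | 8.1–12.0% |
| 0.7 | 11.1–14.3% | 10.7–12.7% |

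Counts with exchangeable correlation and VA adjustment gave 9.9–12.0%. The overall range is 7.8% to 14.3%, which is 7.8/5 ≈ 1.6 to 14.3/5 ≈ 2.9 times nominal.

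**4. Patient as the cluster (counts).** 14.6% to 36.1%.

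**5. Candidate corrections.**

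| Method | Counts | Cox |
|---|---|---|
| Uncorrected, t reference only | 6.5–11.7% | 5.9–10.4% |
| Kauermann-Carroll with t | 4.8–7.9% | not run |
| Mancl-DeRouen with t, 16–17 df | 3.4–5.3% | not run |
| Leave-one-center-out jackknife with t, 16 df | not run | 3.2–5.7% |

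The jackknife row comes from 1,500 trials per setting with 936 patients, VA adjustment, site log-hazard SD 0.15 to 0.3 and site-size CV about 0 to 0.7. In those runs the uncorrected z-test rejected 8.9–13.0%. Degrees of freedom are 19 − 3 = 16 with intercept, treatment and VA, or 19 − 2 = 17 without VA.

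**The case against.** Several objections stand and limit the point.

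- **Silence is not a choice of method.** A reader might infer that the SAP prescribes the uncorrected sandwich with a z-test. It does not; it says only that standard errors are robust. The supportable statement is that no correction is specified, so the uncorrected test is permitted.
- **The size is assumption-driven.** The only ICC in the documents is for FACT-Hep change, and no site counts are given. The protocol synopsis aims for roughly equal recruitment per center, which favors the lower rows of the range. Against that, Protocol 5.2 reports lower enrollment in the hepatologist-led arm, and Protocol 5.4 gives center volumes from 650 to 6,000 ESLD patients a year.
- **More than double the stated error rate.** This reading is tempting but unsupported. The 0.05 level is stated for the primary test, not for these endpoints. With equal sites, the Cox results and most of the count range stay below twice nominal.
- **All utilization results are affected.** They are not. SAP 5.4 analyzes the 30- and 90-day admission proportions by random-effects logistic regression.
- **SAP and protocol contradict each other on survival.** That is too strong. The protocol only says it will consider a frailty model, and the SAP is the document that sets out methods in detail. The two models generally estimate different hazard ratios, so the wording should still be aligned. Survival is exploratory, and the protocol's survival hypothesis is a comparison with historical data.
- **Center is the evident intention for the GEE.** The cluster standard listed in Protocol section 12 supports that reading. It makes patient-level clustering unlikely, but it does not replace a statement in SAP 5.4.

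**Conclusion.** The point holds as a gap in specification. Two sets of analyses, the secondary one-year counts and the exploratory survival comparison, rely on robust standard errors from 19 centers with no small-sample method, and the count analysis does not name its cluster. If the default uncorrected sandwich and z-test are used, the false-positive rate at a nominal two-sided 5% is about 8% to 14%. The lower end applies to equal sites and the upper end to unequal sites, under the assumed event rates and between-site variation listed above. The hand calculation of 8.2% supports the lower end without any event-rate assumption. Nothing here bears on the primary mixed-model analysis. This should be corrected before the analyses are run, but it does not threaten the trial's main conclusion.

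**What to change.** **SAP 5.4.** Name center as the GEE cluster for the count models, include the VA stratum, and use the Mancl-DeRouen corrected sandwich with t on about 16 df (17 if VA is left out). A t reference alone, or Kauermann-Carroll with t, does not reliably restore 5%.

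**SAP 5.5.** Keep the marginal Cox model. Base the treatment p-value and interval on a leave-one-center-out jackknife variance with t on about 16 df. A permutation test of centers is an alternative for the p-value, but it must follow the allocation described in Protocol 5.2: 14 centers within VA strata (4 and 3 in one stratum, 3 and 4 in the other), then five added at 4 to 1. Permuting all 19 centers simply within VA stratum would not match that design.

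**Protocol 11.3.** Align the shared-frailty wording with the SAP so that one survival model is named.

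**Cost.** A few sentences, a different variance option in the programs and no new data. Intervals for these endpoints become somewhat wider.

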5.5 Exploratory Analyses

Survival will be summarized with Kaplan-Meier curves. Cox regression will be used for multivariable models, and robust standard errors will be used to account for within center clustering. ITT population will be used for the survival analyses.

Longitudinal analysis of FACT-Hep total score at 1, 2, 3, 6, 9 and 12 months will be performed utilizing the ITT population. Measurements of Fact-Hep will be set to missing after patients receive liver transplant or are transferred to hospice. A mixed model will be considered with center as a random effect and unstructured covariance structure (alternatively autoregressive covariance structure in case of a convergence difficulty) for repeated measurements of FACT-Hep over time within a patient. As in the primary analysis, the model will have treatment effect and adjustment for baseline FACT-Hep total score and VA status.

Additional covariates will be considered for multivariable modelling. MI will be utilized if more than 10% of missing records are present.

6 SUB-GROUP ANALYSES

For subgroup analyses, the following groups will be evaluated: transplant eligible vs. ineligible, presence of HCC vs. no HCC, and disease severity as assessed by MELD score <20 vs. ≥ 20 . Using multivariable linear mixed models, a potentially differential impact of the intervention will be assessed across complementary subgroups by testing for interaction of the treatment variable with a subgrouping variable by adding terms for the subgroup and its interaction with treatment to the model from the primary analysis. In addition to the test of interaction, we will present estimated treatment effects and the corresponding 95%CI for subgroup treatment effects from this model. These descriptive summaries will be interpreted in conjunction with the formal interaction tests. The main subgroup analyses will be conducted for the primary endpoint.

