2.3 Sample Size Determination and Statistical Power

2.3.1. Sample Size Determination

Patient-reported quality of life, as measured by FACT-Hep total score, is the primary outcome measure in this study. Published estimates show the average performance on this measure for typical patients with ESLD is 143.0 points (SD 20.6) and a difference of 9 points on this measure reflects a minimal clinically meaningful difference (MCID) in QOL [1,2]. However, the power estimates below are based on SD=19.1 for change in FACT-Hep total score from baseline to 3 months observed in the study at the time of sample size re-computation (**n=936**). Patient level data analysis will be considered with adjustment for clustering, i.e., adjustment for correlation of patients' outcomes within a cluster (site). This correlation is quantified by the intraclass correlation coefficient (ICC). At the time of sample size re-computation ICC=0.09 was noted in the study.

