2.3.2. Statistical Power for Superiority Hypothesis

Power for superiority hypothesis is **83.2%** and it is based on the final enrollment in the sites and estimated (as of September 25, 2024) counts of patients evaluable for change in FACT-Hep total score from baseline to 3 months.

Power was derived via simulations utilizing multivariate normal distribution with the earlier mentioned SD=19.1 and ICC= 0.09. Each simulation consists of generating, for each of the 19 sites, the evaluable patient count of realizations from this distribution. Since only difference in means between the two arms matters, for simplicity, the consultative PC sites were considered to have zero mean and the Hepatologist led PC sites to have mean equal to MCID=9. For each simulation a mixed model $\text{change}_{ij} = \alpha + \beta \text{trt}_{ij} + s_j + e_{ij}$ was fit to the simulated data (with $\text{trt}=1$ for Hepatologist led PC-Model 2 and $\text{trt}=0$ for Consultative PC-Model 1) where response change_{ij} is change in FACT-Hep total score from baseline to 3 months for the i -th patient in the j -th site ($j=1,2,\dots,K=19$). Random effects $s_j \sim N(0, \sigma_s^2)$ inducing correlation within sites are assumed to be independent across the sites and also independent from independent random

errors $e_{ij} \sim N(0, \sigma_e^2)$. Proportion (out of 100,000 simulations) of treatment variable p-values less than 0.05 provided estimate of the power for superiority.

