5 EFFICACY ANALYSES

5.1 Primary Efficacy Analyses

The primary analysis will be performed on the mITT population. To account for the cluster-based randomization we will utilize linear mixed model with the treatment arm indicator (binary variable) as a fixed effect and center (cluster) as the random effect. We will also adjust for the baseline FACT-Hep total score and the binary randomization strata variable (VA vs. non-VA). Namely we will consider the model $Y_{ij} = \beta_0 + \beta_1 \text{Treatment} + \beta_2 \text{Baseline FACTHep} + \beta_3 \text{Stratum} + a_j + e_{ij}$ where response Y_{ij} is change in FACT-Hep total score from baseline to 3 months for the i-th patient in the j-th center ($j=1,2,\dots,19$). The random effect of center j is $s_j \sim N(0, \sigma_s^2)$ and is assumed to be independent from random errors $e_{ij} \sim N(0, \sigma_e^2)$. Binary variable "Treatment" is coded as 1 for the hepatologist led PC and 0 for the Consultative PC. Binary variable "Stratum" is coded 1 for VA and 0 for non-VA.

The superiority null hypothesis is $H_0: \beta_1=0$ and alternative hypothesis $H_1: \beta_1 \neq 0$. We will reject the null hypothesis if two-sided P-value is < 0.05 and conclude that treatment has significant effect on change in FACT-Hep total score.

Only if superiority is not demonstrated (i.e., when superiority p-value ≥ 0.05) then the non-inferiority (NI) analysis will be performed. Non-inferiority of Model 2 (Hepatologist led PC) will be demonstrated if the lower two-sided 95% CI limit (L) for β will be greater than negative pre-specified DELTA margin, i.e., when $L > -4.0$.

In addition to the statistical hypothesis testing, 95% confidence intervals descriptively summarizing the difference in outcome between the two treatment arms, as well as outcome in each randomized arm will be computed.

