A complete case analysis will be performed if the primary analysis has $\leq 10\%$ of patients with missing outcome information. If there are more than 10% of patients with missing outcome information, we will utilize multiple imputations (MI) (see section 12.4 for more details). Variables used in multiple imputations will include FACT-Hep total score values measured at baseline, 1 month, 2 months, and 3 months as well as treatment assignment, stratum variable (VA vs. Non-VA), and baseline demographics (including age, gender, education level, employment status, marital status, and smoking status). Change in FACT-Hep total score will be computed with baseline and 3 month FACT-Hep total score values resulting from MI.

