12.4 Handling of Missing Data

Every effort will be made to minimize the extent of missing values by proactive strategies, inevitably we will need to deal with some missing value problems [3]. To prevent and limit

missing data other than due to patient's death or curative therapy prior to completion of the study we will perform data checks and consistency checks during the study and collaborate with sites to complete missing or incorrect data items. If \leq up to 10% of patients have missing data for a particular analysis, we will conduct complete case analysis utilizing only non-missing data. However, if more missing data ($> 10\%$) is present we will utilize multiple imputations (MI) to mitigate potential bias of the complete case analysis and appropriately reflect the uncertainty due to imputations [4]. The MI method assumes that the data are missing at random (MAR), meaning that the probability of missingness depends on observed data but not on unobserved data. An imputation model will be constructed including all variables that are part of the analysis model and additional auxiliary variables (including age, gender, education level, employment status, marital status, and smoking status) that may be predictive of the missingness. Both continuous and categorical variables will be included. Multiple imputation will be performed using the PROC MI procedure in SAS 9.4 utilizing fully conditional specification (FCS) method for data sets with arbitrary missing patterns [5]. A total of 1000 imputations will be performed. Each of the imputed datasets will be analyzed separately, and the results will be combined using SAS PROC MIANALYZE to obtain valid statistical inferences that reflect the uncertainty due to imputations of missing data and account for the variability both within and between the imputed datasets.

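### If multiple imputation is used for the subgroup analyses, the SAP does not call for a treatment-by-subgroup term in the imputation model, so a true interaction can be shrunk toward zero

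*SAP*

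**What the plan says.** SAP section 6 names three subgroup factors (transplant eligible or not, HCC or not, MELD below 20 or not). It tests each on the primary endpoint by "adding terms for the subgroup and its interaction with treatment to the model from the primary analysis", and reports the subgroup treatment effects with 95% confidence intervals. It does not mention imputation.

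SAP 5.1 uses complete cases up to 10% missing outcomes and MI above that. Its variable list for the primary analysis is FACT-Hep at baseline and months 1, 2 and 3, "as well as treatment assignment, stratum variable (VA vs. Non-VA), and baseline demographics". It contains no transplant eligibility, HCC or MELD, and no product term.

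SAP 12.4 applies the 10% threshold analysis by analysis and gives a general rule: "An imputation model will be constructed including all variables that are part of the analysis model and additional auxiliary variables". The method is fully conditional specification (FCS) with 1000 imputations under missing at random.

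**The concern.** An imputation model with main effects only predicts about the same treatment effect in both subgroups. Patients imputed from it carry little of any true difference between subgroups, and they dilute the interaction that section 6 tests. Adding the subgroup as a main effect does not help, because it shifts both arms equally.

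The general rule in SAP 12.4 speaks of variables. A programmer could satisfy it, and the 5.1 list, without a product term. The subgroup tests would then lean toward no differential effect, and the subgroup estimates would look more alike than they are. SAP 12.4 brings in MI to reduce the bias of complete cases; for this analysis it could add bias. The protocol (section 12) also lists among the standards met that heterogeneity analyses have a plan with appropriate methods.

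**Working it through.** **1. The plan's own power.** No power is stated for the interaction tests, so the check starts from the primary test. Inputs: "the power estimates below are based on SD=19.1 for change in FACT-Hep total score from baseline to 3 months"; "At the time of sample size re-computation ICC=0.09 was noted in the study"; "the Hepatologist led PC sites to have mean equal to MCID=9"; "We will reject the null hypothesis if two-sided P-value is < 0.05"; 936 patients at 19 sites (SAP 2); 7+1 = 8 and 7+4 = 11 sites per arm (SAP 2.1). Site-level evaluable counts are not given, so equal sites of n evaluable patients are assumed.

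SE = SD × √[(ICC + (1−ICC)/n) × (1/8 + 1/11)]

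- All 936 evaluable: n = 936/19 = 49.26; SE = 19.1 × √[(0.09 + 0.91/49.26) × 0.2159] = 2.92; 9/2.92 = 3.08. A t reference with 17 df gives 82.7%. For non-inferiority, (4.5 + 4)/2.92 = 2.91 gives 78.2%.
- 60% evaluable: n = 29.56; SE = 3.08; 9/3.08 = 2.92. A normal reference gives 83.1%, and 78.7% for non-inferiority.

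SAP 2.3.2 states "Power for superiority hypothesis is 83.2" per cent, and SAP 2.3.3 states 79.2%. Both settings come within one point, so the figures are reproduced but do not reveal how many patients are evaluable.

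**2. Closed form, worst case.** Let m be the missing fraction and θ the true interaction. If patients missing month 3 have no month 1 or 2 score, observed patients carry θ and imputed patients carry about 0:

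expected estimate = (1−m) × θ + m × 0 = (1−m)θ

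This is 88% of truth at m = 0.12 and 75% at m = 0.25. The test statistic relative to complete cases is √[(1−m)/(1+m)]. Starting from 80% complete-case power (1.96 + 0.84 = 2.80):

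- m = 0.10: 2.80 × 0.905 = 2.53, power 72%
- m = 0.20: 2.80 × 0.816 = 2.29, power 63%
- m = 0.30: 2.80 × 0.734 = 2.06, power 54%

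**3. Simulation with the earlier visits.** From the documents: 936 patients, 8 and 11 sites, ICC 0.09, SD of change 19.1, baseline SD 20.6 (protocol section 8). With equal SDs these imply a baseline to month-3 correlation of 1 − 19.1²/(2 × 20.6²) = 0.57. Assumed: interaction 7 points, subgroup prevalence 40%, missing at random given baseline, and the missing fraction, visit correlation and availability of earlier scores shown below. There were 1200 runs with 20 imputations each, so the Monte Carlo error on power is about √(0.75 × 0.25/1200) = 1.25 points.

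| Missing | Of these, with months 1 and 2 | Correlation of months 1 and 2 with month 3 | Interaction over time | Recovered, no product term | Power: no product term / complete cases / product term |
|---|---|---|---|---|---|
| 12% | none | 0.75 | constant | 89% | 74 / 83 / 83% |
| 25% | none | 0.75 | constant | 75% | 50 / 76 / 73% |
| 25% | half | 0.75 | constant | 85% | 66 / 74 / 76% |
| 25% | 70% | 0.75 | constant | 88% | 72 / 74 / 76% |
| 25% | all | 0.65 | constant | 91% | 74 / 74 / 76% |
| 25% | all | 0.75 | constant | 94% | 78 / 73 / 77% |
| 25% | all | 0.85 | constant | 98% | 83 / 74 / 83% |
| 25% | all | 0.75 | 1/3, 2/3, 1 | 85% | 68 / 73 / 78% |

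Adding the subgroup as a main effect gives the same recovered percentages. With the product term, recovery is 99-101% throughout.

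**4. A second set of assumptions.** With an interaction of 9 points, 45 patients per site, prevalence 35%, an effect growing by thirds, and half of those missing having no follow-up score, main-effects imputation recovers 90%, 83%, 74% and 67% of truth at 12%, 20%, 30% and 39% missing. Imputation by arm recovers 100-101%.

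**The case against.** The strongest reply is that the SAP never says the interaction is left out. The 5.1 list serves a primary model that has no interaction. SAP 12.4 asks for everything in the analysis model, and section 6 defines that model with the interaction in it. This stands in part. A reader might infer that the plan excludes the term, but the documents support only that it is not called for: 12.4 can be read either way.

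A reader might also infer that every interaction estimate is pulled toward zero and that MI always loses power against complete cases. Neither holds. The attenuation is an average and arises only where a true interaction exists. Months 1 and 2 are in the imputation list, and good earlier scores leave power equal or higher (74 v 74%, 78 v 73%, 83 v 74%). On the other side, protocol 5.3 describes month 1 as showing immediate effects and month 3 cumulative ones, which fits the growing-effect row. SAP 5.2 also counts deaths before month 3 as missing outcomes, and some of these patients may have no earlier score.

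A third inference is that MI is likely to be triggered, from back-solving the stated power for evaluable patients. Step 1 shows that this fails: about 83% is obtained with all 936 or with 60% of them, depending on the reference distribution. In addition, the mITT population removes patients with early transplant or hospice transfer, and protocol 11.2 says the counts preceded completion of the 3-month follow-up. Non-evaluable patients out of 936 are therefore not the trigger fraction.

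Finally, these are subgroup analyses with no power target, and the SAP treats the subgroup estimates as descriptive. That limits the consequence.

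**Conclusion.** The point holds as a conditional weakness in specification. If MI is used for section 6 and the imputation has main effects only, which the wording permits, a true treatment-by-subgroup interaction is understated on average. At 25% missing the understatement is 2-9% when months 1 and 2 are fully observed with the same interaction, 15% when they are observed but the effect grows, and 25% when they are absent. The effect on power against complete cases runs from a loss of 26 points (50 v 76%) to a gain of 9 (83 v 74%).

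A null interaction stays null, and the superiority and non-inferiority conclusions are untouched. The missing fraction, subgroup prevalence, interaction size, visit correlations and availability of earlier scores are all assumptions; the documents give none of them. It is worth correcting because the stated rule can be followed exactly and still bias the test toward homogeneity.

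**What to change.** In SAP 6 and 12.4, state that when MI is used for a subgroup analysis, the imputation model for that analysis includes the subgroup variable (transplant eligibility, HCC or baseline MELD group) and its interaction with treatment, or that imputation is run separately by arm with these variables included. Report the complete-case interaction test alongside as a check.

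The 5.1 imputation for the primary estimate need not change. The cost is a separate imputation run for the subgroup models and slightly less precise imputation regressions: in the simulations, power with the product term was between 3 points below and 9 points above complete cases. No new data are needed.
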